7.2. Drug Information on Pembrolizumab

Name of investigational drug:	Pembrolizumab
Dosage form:	Solution
Drug code:	MK-3475
Manufacturer:	MSD K.K.
Content:	100 mg/vial
Dosage:	Pembrolizumab should be diluted with normal saline or 5% glucose solution in a concentration range of 1 to 10 mg/mL, and 200 mg/body should be intravenously administered over 30 minutes.
Route of administration:	Intravenous infusion

Expiration date:	See the Procedures for Investigational Drug Management.
Labeling:	
On the outer box, the investigational drug code, content, lot number, expiration date, quantity, storage method, and the names, job titles and addresses of the coordinating investigators, as well as the fact of being clinical study use only are mentioned.
 
The job titles of the coordinating investigators to be indicated on the outer box should be those at the time of the start of the study and should not be changed even if they are changed during the study.

Storage method for the drug:	Store in a tight, light-resistant container at 2 to 8°C.

Pembrolizumab will be provided free of charge by, a supplier of the investigational drug, MSD K.K. The supplier of the investigational drug will also provide manufacturing and quality study records of the investigational drug, and pembrolizumab solution.

7.3. Management of Study Drugs

Lenvatinib will be supplied by Eisai to National Cancer Center Hospital East. Pembrolizumab will be supplied by MSD to National Cancer Center Hospital East. The Study Drug Manager of each study site will appropriately control the study drugs in accordance with the procedures for study drug management provided by the coordinating committee.

The investigator (subinvestigator) will prescribe the study drugs at doses specified in the protocol, and intravenously or orally administer to subjects. The study drugs must not be administered by other methods than those specified in the protocol.

7.4. Expected AEs

Expected AEs associated with lenvatinib and pembrolizumab are defined as follows: Events, of which the onset or onset trend such as the number of cases, frequency and onset conditions are not expected from the investigator's brochure of the investigational drug using the latest investigator's brochure as a reference, are defined as "unknown," and those which are expected are defined as "known." However, new events reported to the study sites can be handled as "known" even if they are not listed on the investigator's brochure.

8. ENDOPoints, LABORATORY TESTS AND EVALUATION SCHEDULE

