2.11. Summary of Expected Benefits and Disadvantages Associated with the Study Participation

In this study, if combination therapy with lenvatinib and pembrolizumab in patients with gastric cancer is judged to be effective, a prospective treatment regimen can be expected for a larger number of participating subjects.

The anticipated disadvantages include any adverse events associated with lenvatinib and pembrolizumab. To minimize the risk and disadvantages of adverse events, the data center together with the Data and Safety Monitoring Committee will monitor any adverse events in the present trial to determine whether or not they are within the expected range. These bodies will also conduct a thorough examination in the event that serious or unexpected adverse events occur, and adopt an appropriate system to take any necessary actions.

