10.2.3. Reporting Obligation of the Coordinating Committee and Reporting Procedures

The coordinating committee should determine the seriousness, causal relationship, expectedness and the necessity for reporting to the regulatory authority (Pharmaceuticals and Medical Devices Agency (PMDA)) (pursuant to “Article 80-2, Paragraph 6 of the Pharmaceutical Affairs Law (PAL)” and “Article 273 of the Enforcement Regulations of the PAL”) for SAEs notified by initial and additional reports.

The details of reporting procedures should be as specified in the “Procedures for Handling

of Safety Information."

1) Report to each principal investigator

The coordinating committee should promptly report the notified SAE with the details of the abovementioned determinations to each principal investigator. Each principal investigator should, as necessary, report them as soon as possible to the head of the study site in accordance with rules at each study site.

2) Report to the PMDA

When reporting to the PMDA is found necessary, the coordinating committee should handle the matter in accordance with Article 273 of the Enforcement Regulations of the PAL and relevant notifications.

3) Report to the efficacy and safety evaluation committee

When a review of an SAE by the efficacy and safety evaluation committee is judged to be necessary, the coordinating committee should report it in writing and seek its opinions on the appropriateness of the comments of the principal investigator and coordinating committee on the AE and handling (assessments of the seriousness, causal relationship and expectedness of the AE) of the AE.

4) Report to the investigational drug suppliers

The coordinating committee should promptly notify SAEs reported by the investigator to the investigational drug suppliers. In addition, the coordinating committee should, as necessary, provide information other than the "SAE Report" to the investigational drug suppliers upon their request.

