10.3. Collection of Safety Information

When safety information on the investigational drugs is received from the investigational drug suppliers, the coordinating committee should handle it in accordance with Article 273 of the Enforcement Regulations of the PAL and relevant notifications. The coordinating committee should report the safety information to each principal investigator. Each principal investigator should report it to the head of the study site as soon as possible in accordance with rules at each study site.

For the details of reporting procedures, the “Procedures for Handling of Safety Information” should be followed.

In addition, the necessity of revising the protocol and written information to patients as well as an explanation to the patients should be determined and implemented if needed.

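### Section 7.4 permits, without stated limits, repeats of an event absent from the investigator's brochure to be classed as known once the event has been reported to the study sites

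*Combined protocol and SAP*

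**What the plan says.** Section 7.4 takes the latest investigator's brochure as its reference. An event is *unknown* when its "onset or onset trend such as the number of cases, frequency and onset conditions are not expected" from that brochure; otherwise it is *known*. The test therefore covers more than listing: a listed event that occurs too often can also be *unknown*.

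The last sentence of 7.4 adds an exception. "However, new events reported to the study sites can be handled as" *known* "even if they are not listed on the investigator's brochure".

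Three other sections bear on the label:

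- Section 10.2.3, on SAEs notified to the committee: "The coordinating committee should determine the seriousness, causal relationship, expectedness and the necessity for reporting to the regulatory authority". Item 1) continues: "The coordinating committee should promptly report the notified SAE with the details of the abovementioned determinations to each principal investigator". Under item 3), the efficacy and safety evaluation committee comments on expectedness only when the coordinating committee considers its review necessary.
- Section 10.3, on safety information from the suppliers: "The coordinating committee should report the safety information to each principal investigator".
- Section 2.11 says that the data center and the Data and Safety Monitoring Committee will "conduct a thorough examination in the event that serious or unexpected adverse events occur".

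**The concern.** An exception that turns on whether an event has been circulated can undercut a definition that turns on what the brochure predicts. The protocol's own circulation steps can meet the exception's condition after a single serious case. A second or third case of an unlisted event may then be labelled *known* while the brochure is still silent on it.

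This matters because repetition of an unlisted event is an informative safety signal in this trial. Section 2.5.1 says that the authors knew of no study of lenvatinib with an anti-PD-1 antibody in advanced gastric cancer, and the phase 1b experience it describes is 13 patients with solid tumors. Study interruption under 15.4.1 depends on adverse events exceeding an acceptable range that has no numerical limit, so case-by-case classification carries some weight. With no limit on the exception, two assessors could also label identical cases differently.

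**Working it through.** The plan gives no figure on this point, so the main check is a comparison of the text.

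**1. The two parts of 7.4, applied to a second case of an unlisted event after the first has been circulated**

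| | Opening definition | Last sentence |
|---|---|---|
| What it looks at | Onset and onset trend against the brochure | Whether the event has been reported to the sites |
| Label | *Unknown*, if the brochure does not predict the onset or the number of cases | *Known* is permitted |
| Force | Definition | Option |
| Stated limit | Latest brochure | None |

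The last sentence does not say who must have reported the event, how many cases are needed, whether a brochure revision must follow, or whether a later rise in frequency makes the event *unknown* again. Section 7.4 does not rank the two parts, and nothing in Section 10 limits the exception.

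**2. Can the trial's own process meet the condition?** Yes, by two routes. Section 10.2.3(1) sends each notified SAE to each principal investigator, so one serious case can suffice. Section 10.3 does the same for supplier information. No equivalent route is stated for non-serious events arising in the trial. A non-serious case could be affected if the same event had already been circulated as an SAE or in supplier information.

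**3. What depends on the label?**

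| Step | Depends on expectedness? |
|---|---|
| SAE to site head and coordinating committee within 24 hours (10.2.2) | No |
| SAE to the manufacturer's safety group (10.2.1) | No |
| SAE onward to principal investigators and suppliers (10.2.3) | No |
| Tabulation of adverse events in the safety population (12.6) | No |
| Expectedness determination, made with the need to report to the regulator (10.2.3) | The label is the determination; its effect on regulator reporting is not stated |
| Thorough examination (2.11) | Only for non-serious events, since serious ones qualify anyway |

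**4. Illustration of size, as an upper limit.** Assumptions: n = 29 (the planned FAS), at most one case per patient, and a true incidence p of an unlisted event, which the documents do not give. With N binomial(29, p):

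- P(N ≥ 1) = 1 − (1 − p)^29
- P(at least one repeat) = P(N ≥ 2) = 1 − (1 − p)^29 − 29p(1 − p)^28
- Expected repeats = 29p − P(N ≥ 1)

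| Assumed p | Expected cases, 29p | P(N ≥ 1) | P(N ≥ 2) | Expected repeats |
|---|---|---|---|---|
| 1% | 0.29 | 0.253 | 0.034 | 0.04 |
| 3% | 0.87 | 0.587 | 0.216 | 0.28 |
| 5% | 1.45 | 0.774 | 0.429 | 0.68 |
| 10% | 2.90 | 0.953 | 0.801 | 1.95 |
| 20% | 5.80 | 0.998 | 0.987 | 4.80 |

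For p = 5%, expected repeats are 1.45 − 0.774 = 0.68. All repeats would be relabelled only if the first case had been circulated before the second arose and the option were always used.

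**The case against.** A reader might infer that every repeat after the first case automatically stops counting as unexpected. The text does not support that. The exception is permissive, and under 10.2.3 the coordinating committee determines expectedness for notified SAEs and may keep the label *unknown*. The trigger is the report to the sites, not the first case, so a second case that arises before circulation is unaffected. Section 10.2.3(1) circulates SAEs only.

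The two parts of 7.4 can also be read together: circulation may make up for an event not being listed, while an unexpected cluster remains *unknown* on the onset-trend test. That reading is reasonable, but 7.4 does not state it.

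The exception may have been meant mainly for supplier information received between brochure updates. The synopsis names one planned site, where an in-trial event would be reported by the site rather than to it, although Section 16 calls the study multicenter. The wording does not restrict the source, so the in-trial route stays open.

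A reader might further infer that repeat SAEs would go unreported, or that reports to the regulator would be missed. The first is contradicted by 10.2.1 to 10.2.3, where SAE reporting within the trial and to the suppliers does not depend on expectedness. The second cannot be shown. The cited regulations and the separate procedures for handling safety information are not part of the documents, and those procedures may add limits.

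These points narrow the concern considerably. What stands is an exception with no stated limits whose relation to the definition it qualifies is left open.

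**Conclusion.** The point holds as a gap in the rule for classifying events; it does not demonstrate a safety failure. The label can be changed by circulation alone, and its priority over the onset-trend test is unstated. The exposure is the expectedness determination in 10.2.3 and, mainly for non-serious events, the unexpected-event trigger in 2.11.

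The chance that at least one repeat case arises in 29 patients runs from 3% at an assumed incidence of 1%, through 43% at 5% and 80% at 10%, to 99% at 20%. These are upper limits on how often a relabelling could occur, and they rest on incidences that the documents do not supply. The conclusion about the text does not depend on them.

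**What to change.** Delete the last sentence of 7.4, and state that expectedness is assessed against the brochure version in force at onset.

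If the sponsor-investigator wishes to keep the exception, the minimum is one added sentence: circulation to the sites does not make an event *known* when its number of cases, frequency or onset conditions are not expected from the brochure. In either case, align 10.2.3 by referring its expectedness determination to the revised 7.4, and check the separate safety-information procedures for consistency.

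The cost is a short text change. The downside is that a few more events will be assessed as unexpected until the brochure is revised.

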8.1. Observations and tests

Each endpoint in this study is presented below. All data required by the protocol should be recorded.

Table 8.1 Observations and tests

Treatment compliance	Doses of lenvatinib and pembrolizumab, date of first dose, date of last dose or date of discontinuation (treatment interruption), presence/absence of dose change and its reason, and presence/absence of treatment interruption, its frequency and its reason
Patient background characteristics	Sex, age, past history, complications, histology (pap, tub1, tub2, por1, por2, sig, muc or other), HER2, EBV, PD-L1, presence or absence of the primary lesion, lesion site (primary site, target lesion, nontarget lesion) and presence or absence of previous treatment and its details
Physical examination	Body height and weight
Vital signs	Body temperature, pulse rate, systolic and diastolic blood pressure
General condition	PS(ECOG)
AEs	Presence/absence and severity of AEs will be evaluated in accordance with the CTCAE v 4.0.
Concomitant medications/therapies	Name of drug, route of administration, start date of treatment, end date of treatment and reason for concomitant use
Hematology	Red blood cell count, Hb, hematocrit, White blood cell count, neutrophil count, and platelet count
Biochemistry	AST(GOT), ALT(GPT), ALP, LDH, albumin, total bilirubin, BUN, creatinine, CK, electrolytes (Na, K, Cl, Ca), Amy, UA, blood glucose, CRP
Blood coagulation test	PT, INR, APTT
Thyroid function	Thyroid stimulating hormone, free triiodothyronine (fT3), and free thyroxine (fT4)
Tumor markers	CEA, CA19-9
Urinalysis	Urine protein, urinary sugar and urinary occult blood
Pregnancy test	If pregnancy is suspected by urinalysis, a serum test It will be performed in premenopausal women or women who had the last menstruation no more than one year
ECG	12-lead resting ECG
Infection	HIV antibody, HBs antigen, HBC antibody, HBs antibody, HCV antibody, HBV-DNA

Tumor assessment	
Chest and abdomen/pelvic contrast CT* or abdomen/pelvic contrast MRI*, as necessary, chest radiography, brain CT and brain MRI
 
* For patients who are allergic or have hypersensitivity to contrast media to be used for CT and MRI, the tests may be performed without using the contrast media.
 
When the treatment is discontinued because of reasons other than the progression of the primary disease based on imaging, the assessment should be made until progression is confirmed.

Investigation of outcome	
Presence or absence of subsequent treatment, if subsequent treatment is given, a treatment method and start date
 
Date of death or the last day of survival confirmed, and if died, the cause of death

8.2. Observation and schedule

The observation and testing schedule is presented in Table 8.2. When the principal investigator (or subinvestigator) deems it necessary to perform additional tests or observations, they will be performed in addition to the schedule presented in Table 8.2.

Table 8.2. Schedule

	At enrollment	During protocol treatment					Day of discontinuation ^{e)}	days after the last dose ^{f)}	After the follow-up period
		Cycle1		Cycle2 onwards					
Day Permissible range	-14~	1	8	15	1	15 ^{d)}	0~+7	-3~±7	
Visit	○	○	○	○	○	○	○	○	○
Informed Consent	○								
Treatment									
Lenvatinib Treatment		○	→	→	○	→			
Pembrolizumab treatment		○			○				
Patient background characteristics	○								

Body measu remen ts	Height	○								
	Weight	○	○ ^{c)}			○		○	○	
Vital signs ECOG PS		○	○	○	○	○	○	○	○	
Clinical findings (including AEs) Concomitant medications/con comitant therapie				→	→	→	→	→	→	
Laboratory tests										
Blood tests (blood count, biochemistry)		○	○ ^{c)}	○	○	○	○	○	○	
Urine analysis	○	○ ^{c)}	○	○	○	○	○	○	○	
Thyroid function	○	○ ^{c)}			○					
Blood Coagulation test	○	○ ^{c)}			○					
Pregnancy test ^{a)}	○									
Tumor markers	○	○ ^{c)}			○		○			
12-lead ECG	○						○	○		
Infection test	○ ^{b)}									
Tumor evaluation										
Chest/abdomina l/pelvic CT (MRI) and other evaluations ^{g)}	○	Conducted at every 6 weeks after the start of treatment						△		
Follow-up										
Outcome investigation										○

O: Essential item, Δ:Performed as needed

- a) Limited to women capable of childbearing. Refer to section 8.4.3
- b) Tests conducted within 6 months of enrollment can be alternatively used.
- c) Pre-enrollment tests (7 days before drug administration) can be used as tests conducted on day 1 (pretreatment).
- d) From 3 cycle onwards, the implementation of day 15 is unnecessary unless the investigator considers clinically necessary.
- e) The day of termination is defined as the day when the principal investigator (or subinvestigator) decides to terminate the subject's administration of the investigational drug. When observations and tests cannot be conducted because of the subject's condition, they should be conducted as soon as possible.
- f) Follow-up tests for safety are conducted 30 days after the last dose of the investigational drug. When observations and tests cannot be conducted because of the subject's condition, they should be conducted as soon as possible. When a new anticancer drug is initiated within 30 days of the last dose of the investigational drug, the follow-up tests for safety are to be conducted before initiating the new anticancer treatment. If the subject cannot come to hospital before the start of the new anticancer treatment, information will be collected by telephone regarding any new safety issues arising after tests upon completion of the last dose and before initiation of treatment with the new anticancer treatment.
Furthermore, when the follow-up tests of safety are conducted <2 weeks after the tests conducted at the time of the last dose of the investigational drug, the tests conducted at the time of the last dose of the investigational drug and the follow-up tests of safety can be conducted simultaneously.
- g) Refer to section 8.6.

In screening, the results within 21 days before the trial registration are allowed to be used.

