6.3.2. Criteria for Changes in Pembrolizumab therapy

6.3.2.1 Dose modification of Pembrolizumab

For AEs (whether serious or non-serious) related to pembrolizumab exposure, immunological factors may be involved. Such AEs may occur immediately after the start of investigational drug administration or several months after the last dose. For toxicity and

severe or life-threatening AEs related to pembrolizumab, pembrolizumab therapy should be interrupted or discontinued in accordance with Table 6.3.2.1.

Table 6.3.2.1. Dose modification of Pembrolizumab

General instructions:			
Immune-related AEs	Toxicity grade or conditions (CTCAEv4.0)	Action taken to pembrolizumab	Monitor and follow-up
Pneumonitis	Grade 2	Withhold	
 Monitor participants for signs and symptoms of pneumonitis Evaluate participants with suspected pneumonitis with radiographic imaging and initiate corticosteroid treatment Add prophylactic antibiotics for opportunistic infections
	Grade 3 or 4, or recurrent grade 2	Permanently discontinue	
Diarrhea / colitis	Grade 2 or 3	Withhold	
 Monitor participants for signs and symptoms of enterocolitis (i.e. diarrhea, abdominal pain, blood or mucus in stool with or without fever) and of bowel perforation (i.e. peritoneal signs and ileus). Participants with \geq Grade 2 diarrhea suspecting colitis should consider GI consultation and performing endoscopy to rule out colitis.
	Grade 4	Permanently discontinue	

			
 Participants with diarrhea/colitis should be advised to drink liberal quantities of clear fluids. If sufficient oral fluid intake is not feasible, fluid and electrolytes should be substituted via IV infusion.
AST / ALT elevation or Increased Bilirubin	Grade 2	Withhold	
 Monitor with liver function tests (consider weekly or more frequently until liver enzyme value returned to baseline or is stable)
	Grade 3 or 4	Permanently discontinue	
Type 1 diabetes mellitus (T1DM) or Hyperglycemia	Newly onset T1DM or Grade 3 or 4 hyperglycemia associated with evidence of β -cell failure	Withhold	
 Monitor participants for hyperglycemia or other signs and symptoms of diabetes.
Hypophysitis	Grade 2	Withhold	
 Monitor for signs and symptoms of hypophysitis (including hypopituitarism and adrenal insufficiency)
	Grade 3 or 4	Withhold or permanently discontinue ¹	

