For type 1 diabetes mellitus, and Grade 3 to 4 hyperglycaemia with metabolic acidosis or ketonuria, insulin replacement therapy should be considered.

Serum glucose levels and metabolic laboratory values (urine ketone, glycohemoglobin and C-peptide) should be assessed.

Hypophysitis:

In case of Grade 2, corticosteroid should be administered. If the symptom recovered to Grade 1 or lower, the corticosteroid dose should be tapered over 4 or more weeks. Since corticosteroid is administered as tapering the dose, appropriate hormone replacement therapy may be required.

In case of Grade 3 to 4, intravenous corticosteroid followed by oral corticosteroid should be administered. If the symptom recovered to Grade 1 or lower, the corticosteroid dose should be tapered over 4 or more weeks. Since corticosteroid is administered as tapering the dose, appropriate hormone replacement therapy may be required.

Hyperthyroidism and hypothyroidism:

Thyroid dysfunction may occur at any time during dosing. Whether or not there is any change in thyroid function test values (Conduct at the start of the administration of the investigational drug, thereafter periodically and as necessary based on clinical evaluation.) and sign or symptom of thyroid dysfunction should be observed.

Grade 2 hyperthyroidism (and Grade 3 to 4 hypothyroidism):

For hyperthyroidism, non-selective β blockers (e.g., propranolol) are recommended as first-line drugs.

For hypothyroidism, thyroid-hormone replacement therapy with levothyroxine or liothyronine is recommended as standard therapy.

Grade 3 to 4 hyperthyroidism:

Intravenous corticosteroid followed by oral corticosteroid should be administered. If the symptom recovered to Grade 1 or lower, the corticosteroid dose should be tapered over 4 or more weeks. Since corticosteroid is administered as tapering the dose, appropriate hormone replacement therapy may be required.

Liver:

In case of Grade 2, liver function tests should be performed frequently until values returned to baseline levels (Consider implementing the test every week.).

Intravenous or oral corticosteroid should be administered.

In case of Grade 3 to 4, intravenous corticosteroid should be administered over 24 to 48 hours.

If the symptom recovered to Grade 1 or lower, the corticosteroid dose should be tapered over 4 or more weeks.

Renal failure or nephritis:

In case of Grade 2, corticosteroid should be administered.

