12.2. Definitions of Analysis Populations

Each analysis population is defined as follows:

Abbreviation	Analysis population	Definition
All Enrolled Patients (ITT)	Intention to treat	Analysis target group based on the principle of Intention to treat. A population of enrolled patients excluding those with overlapping or incorrect enrollment
SP	Safety Population	A population of all enrolled patients who received at least one dose of the protocol treatment
FAS	Full Analysis Set	A population of all enrolled patients who met the entry criteria and received protocol treatment

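### No thyroid test is scheduled after Day 1 of the last cycle, so patients who stop before Cycle 2 enter the AE denominator with no scheduled post-dose thyroid test.

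*Combined protocol and SAP*

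**What the plan says.** Table 8.2 in Section 8.2 marks thyroid function at enrolment, at Cycle 1 Day 1 and at Day 1 of Cycle 2 onwards: "Thyroid function ○ ○ ^{c", then the later Day 1 mark. The discontinuation and 30-day columns are blank. On the Cycle 1 Day 1 value, footnote c says: "Pre-enrollment tests (7 days before drug administration) can be used as tests conducted on day 1 (pretreatment".

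Other rows of the table do extend to the end visits. Blood count and biochemistry, urinalysis, vital signs and ECG are marked at both, and tumour markers at discontinuation. Footnote f sets the last safety visit: "Follow-up tests for safety are conducted 30 days after the last dose of the investigational drug".

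Section 6.3.2.2 says: "Thyroid dysfunction may occur at any time during dosing". It asks for thyroid tests at the start of dosing, then at intervals and when clinical evaluation calls for them. Section 6.3.2.1 adds that pembrolizumab-related AEs can appear months after the final dose. Its table has a row each for hyperthyroidism and hypothyroidism.

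Section 10.1.6 runs AE collection from the first dose to 30 days after the last, or to the start of subsequent treatment if that is earlier. Events judged related are collected beyond that. Section 11.2.5 takes all treated patients as the denominator for AE incidence. Section 12.2 defines the Safety Population (SP) as: "A population of all enrolled patients who received at least one dose of the protocol treatment". No post-dose laboratory value is required for membership.

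**The concern.** The thyroid schedule stops earlier than the period over which thyroid AEs are counted. A patient who leaves treatment in Cycle 1 contributes to the denominator with no planned opportunity for a silent thyroid abnormality to be found. A patient who leaves later has an unmonitored stretch at the end of the window, which is when delayed immune-related effects could show.

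If such cases are not picked up clinically, the reported incidence of thyroid dysfunction is too low, and more so for patients with short exposure. The planned summary of laboratory changes (Section 12.11.1) would also have no scheduled post-baseline thyroid value for the earliest stoppers. Safety is a secondary endpoint, and Section 12.4 makes safety part of judging whether the treatment is promising.

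**Working it through.** The plan states no figure for this point, so the check is a reading of the table followed by date arithmetic.

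**1. Are the blanks real?** Compare the thyroid row with its neighbours in Table 8.2. The tumour marker row starts the same way ("Tumor markers ○ ○ ^{c") and goes on to a mark at discontinuation. The urinalysis row ("Urine analysis ○ ○ ^{c") goes on to marks at both discontinuation and 30 days. The columns align, so the missing thyroid marks do not look like a fault of text extraction. The coagulation row has the same blanks.

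**2. First scheduled post-dose test.** Cycle 1 Day 1 is pre-treatment and Days 8 and 15 are blank, so the first is Cycle 2 Day 1. With 21-day cycles that is about 21 days after the first dose. A patient who stops before it has 0 scheduled post-dose thyroid tests and still counts as 1 in the SP.

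**3. Gap for later stoppers.** Let d be the cycle day of the last dose, in the last cycle in which a dose is given. The last scheduled test is on Day 1 of that cycle, and the AE window closes 30 days after the last dose if no subsequent treatment starts.

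Gap = (d − 1) + 30 days

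| Day of last dose, d | Gap (days) |
|---|---|
| 1 | 0 + 30 = 30 |
| 8 | 7 + 30 = 37 |
| 15 | 14 + 30 = 44 |
| 21 | 20 + 30 = 50 |

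Lenvatinib is taken daily, so d can be any day of the cycle.

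**4. What this could do to a reported rate (illustration only).** The documents give neither the number k of patients without a post-dose test nor the true incidence. Assume 29 treated patients (the planned Full Analysis Set total), the same true incidence in tested and untested patients, and no case detected among the untested. Then:

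observed incidence = true incidence × (29 − k)/29

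| k | Factor | A true 30% is seen as |
|---|---|---|
| 1 | 28/29 = 0.966 | 29.0% |
| 3 | 26/29 = 0.897 | 26.9% |
| 5 | 24/29 = 0.828 | 24.8% |

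The assumption of no detection among the untested makes the loss look larger than it need be, because clinically suspected cases can still be tested. Early stoppers also have less exposure, so their true incidence may be lower than that of the others.

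**5. Does other text close the gap?** Section 6.3.2.2 calls for periodic and clinically prompted tests but names none at the end of treatment. Sections 8.2 and 8.4.1 allow further tests when judged necessary. Section 8.4.1 refers to a Table 9 and a Table 10 for items and timing. Those numbers do not match the laboratory tables, which leaves Table 8.2 as the operative schedule. None of these passages requires a thyroid test after the last Day 1.

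**The case against.** The strongest reply is that the plan already provides for thyroid monitoring. Testing every 21 days on treatment is periodic, as Section 6.3.2.2 asks, and that section speaks of dysfunction during dosing. Investigators may add tests, and AE enquiry continues through both end visits. Related events are collected even after the 30 days. This stands as far as it goes: symptomatic or suspected cases can be found, and the documents do not flatly contradict themselves.

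A reader might infer several stronger things that the documents do not support.

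- *That testing happens only once symptoms appear.* Section 6.3.2.2 also covers periodic testing and changes in thyroid values.
- *That every untested patient is a lost AE.* Section 10.1.2 counts an isolated laboratory abnormality as an AE only if the investigator finds that it causes signs or symptoms, is clinically important, needs treatment or an additional test, or requires discontinuation or dose reduction. Many silent shifts would not qualify even if measured.
- *That a fixed block of about seven weeks, or the whole AE window for a one-cycle patient, goes unobserved.* The gap varies from 30 to 50 days and is shorter if subsequent treatment starts. A share of calendar time is not a bias in a rate.
- *That many patients are affected.* First imaging is at week 6 (Section 8.6), after Cycle 2 Day 1. Stopping earlier would usually mean clinical progression, toxicity, withdrawal or death. No count is given.
- *That a denominator of tested patients would repair the rate.* It would select patients who stayed on treatment to Cycle 2, and it would leave the gap after the last test as it is.

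It is also fair to say that an all-treated denominator is conventional, that no planned analysis relates thyroid events to time on drug, and that the by-patient laboratory listing in Section 12.11.1 would show who lacks a value.

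**Conclusion.** The point holds as a small gap in ascertainment. Patients who stop before Cycle 2 Day 1 have no scheduled post-dose thyroid test. For later stoppers, 30 to 50 days can separate the last scheduled test from the end of the AE window. That range assumes a last dose between Day 1 and Day 21 of the final cycle and no subsequent treatment within the window.

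What may be missed is asymptomatic or clinically unsuspected thyroid dysfunction that would meet the Section 10.1.2 conditions, in patients who remain in the denominator. The direction is towards under-reporting. The size cannot be estimated from the documents, and the dilution figures above are illustrations under stated assumptions. The primary ORR analysis, the sample size and the two-stage decision rule are unaffected. This is a cheap improvement to a secondary safety endpoint. It is not a defect that threatens the trial's conclusions.

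**What to change.** Reconcile Table 8.2 with Sections 6.3.2.1, 6.3.2.2 and 10.1.6 by marking TSH, fT3 and fT4 in the discontinuation and 30-day columns, using the blood already drawn there. The cost is at most about 29 × 2 = 58 extra panels, fewer where footnote f lets the two visits be combined. There is no additional visit, and the only downside is a small assay cost.

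In Section 12.6, keep the all-treated denominator for AE incidence and add one line giving the number of SP patients with at least one post-dose thyroid test. Label it descriptive: it shows how many patients counted as event-free were never tested, but it does not correct the incidence. If the schedule is left as it is, that line is still worth having, with the same caveat. Neither change affects dosing, treatment or stopping rules.
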